6.0 TREATMENT PLAN

6.1 Drug Administration

Up to 2 cycles of continuous infusion blinatumomab will be given based on the end of Cycle 1 disease response. Cycle 2 of blinatumomab can be given to subjects who have achieved remission (< 5% marrow blasts) after Cycle 1 but have persistent disease identified by multi-parameter flow cytometry (minimal residual disease (MRD) positive $\geq 0.01\%$) after Cycle 1. Additionally, subjects who achieved MRD negativity after Cycle 1 but are unable to proceed to HCT based on the timing/scheduling of the donor collection, a 2nd cycle of blinatumomab may be given. This additional cycle of blinatumomab for subjects awaiting donor collection, may be 28 days but can be less if the HCT is ready to proceed (e.g. 14-day blinatumomab infusion).

Minimal Organ Functions to be Met Before the Start of the Blinatumomab Infusion

Patients must meet the following criteria (prior to blinatumomab infusion)

- No oxygen requirement with oxygen saturations $> 90\%$.
- AST, ALT $< 5x$ upper limit of normal for age; bilirubin < 2 mg/dL.
- Hemoglobin > 8 mg/dL prior to infusion. (May be transfusion dependent).
- Renal function: serum creatinine $< 2 \times$ normal for age.
- Exhibit overt hematologic manifestations of relapse or persistent disease. Evidence of recurrent/persistent disease based primarily on flow cytometry, cytogenetics, chimerism analysis, or other molecular studies does not by itself represent grounds for exclusion.

Blinatumomab will be given as a 28-day continuous infusion with 14-days in between Cycle 1 and Cycle 2 as per the package insert and FDA approved labeling.

Cycle	Patient Weight Greater Than or Equal to 45kg (Fixed-dose)	Patient Weight Less Than 45kg (BSA-based dose)
1: Days 1-28	28 mcg/day	15 mcg/m ² /day (not to exceed 28 mcg/day)
Days 29-42	14-day treatment-free interval	14-day treatment-free interval
2: Days 1-28	28 mcg/day	15 mcg/m ² /day (not to exceed 28 mcg/day)
Days 29-42	14-day treatment-free interval	14-day treatment-free interval

Hospitalization is recommended for the first 3 days of Cycle 1 and the first 2 days of Cycle 2 (if needed).

Pre-medicate with prednisone or equivalent for MRD-positive B-cell Precursor ALL.

For patients \geq 18 years of age, pre-medicate with prednisone 100 mg intravenously or equivalent (e.g., dexamethasone 16 mg) 1 hour prior to the first dose of blinatumomab in each cycle.

For pediatric patients (<18 years of age), pre-medicate with 5 mg/m² of dexamethasone, to a maximum dose of 20 mg prior to the first dose of blinatumomab in Cycle 1 and when restarting an infusion after an interruption of 4 or more hours in the first cycle.

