4.2 Inclusion Criteria

4.2.1 Diagnosis of B-ALL in hematologic complete remission (defined as an M1 marrow, < 5% blasts) with MRD in the bone marrow ($\geq 0.01\%$) by multi-parameter flow cytometry and that meets one of the following:

- Patients in first relapse or greater;

OR

- Patients with very-high risk biology ALL that is proceeding to HCT in first remission (e.g. Induction failure, Severe-hypodiploidy, Ph-like ALL);

OR

- Patients who have persistent MRD after Consolidation therapy (End of Consolidation (EOC) MRD positive $\geq 0.01\%$);

AND with the intent of going on to an allogeneic hematopoietic cell transplantation (HCT) independent of this study

- 4.2.2 Patients must have an available donor and have intention of proceeding directly to HCT after completion of 1 to 2 cycles of Bridging therapy with blinatumomab.
- 4.2.3 Age \leq 25 years at time of study enrollment
- 4.2.4 Karnofsky Performance Status \geq 50% for patients 16 years and older and Lansky Play Score \geq 50 for patients under 16 years of age (see Appendix 1)
- 4.2.5 Have acceptable organ function as defined within 7 days of study registration:

Renal: creatinine clearance \geq 60 mL/min/1.73m² **or** serum creatinine based on age/gender as follows:

Age	Maximum Serum Creatinine (mg/dl)	
	Male	Female
1 month to < 6 months	0.4	0.4
6 months to < 1 year	0.5	0.5
1 year to < 2 years	0.6	0.6
2 years to < 6 years	0.8	0.8
6 years to < 10 years	1.0	1.0
10 years to < 13 years	1.2	1.2
13 years to < 16 years	1.5	1.4
\geq 16 years	1.7	1.4

Hepatic: ALT < 5 x upper limit of normal (ULN) and total bilirubin \leq 1.5 x upper limit of normal (ULN) for age

Cardiac: left ventricular ejection fraction \geq 40% by ECHO/MUGA

- 4.2.6 At least 7 days must have elapsed from prior chemotherapy.
- 4.2.7 Patients who have experienced their relapse after HCT are eligible, provided they have no evidence of acute or chronic Graft-versus-Host Disease (GVHD) and are off all transplant immune suppression therapy for at least 7-days (e.g. steroids, cyclosporine, tacrolimus). Steroid therapy for non-GVHD and/or non-leukemia therapy is acceptable.

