5.1.3 Pretreatment Period

Screening Assessments: The screening procedures and assessments must be completed within 14-days of the Day 1 visit (or the first day of blinatumomab infusion).

- Physical examination
- Vital signs
- Complete medical history
- Baseline conditions assessment
- Documentation of disease assessment (disease-specific staging criteria)
- Performance status (ECOG, KPS, etc.)
- Measurable disease
 - Bone marrow aspirate and/or biopsy (morphology, cytogenetics, FISH and minimal residual disease (MRD) via HTS and flow cytometry). Baseline blast samples will be sent for B-cell and T-cell clonality HTS assessment, since B-lymphoblasts may have detectable T cell receptor (TCR) clones. If T-cell clonal sequences are detected on the baseline sample, T-cell clonality will continue to be sent along with B-cell clonality on subsequent samples (Note that prior MRD by HTS is required, but does not need to be completed within the 14 day window).

- Lumbar Puncture (CSF cytology and cell count)
- History of prior treatments and any residual toxicity relating to prior treatment
- Baseline medications taken within 14-days of Day 1
- Complete blood count (CBC) with differential and platelet count
- Blood chemistry assessment, including:
 - Alkaline phosphatase, aspartate aminotransferase/alanine aminotransferase (ALT/AST), total bilirubin, calcium, phosphorus, blood urea nitrogen (BUN), creatinine, total protein, albumin, glucose, potassium, sodium, chloride, bicarbonate, uric acid, lactate dehydrogenase (LDH).
- Coagulation assessment, including prothrombin time, partial thromboplastin time, international normalized ratio (PT/PTT/INR)
- Urinalysis
- Serum or urine pregnancy test (if applicable) within 7-days prior to the start of blinatumomab
- Electrocardiogram (EKG)
- Cardiac assessment (ECHO, MUGA, etc.)
- CMV serology and EBV serology prior to the start of the first cycle of blinatumomab

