5.2 Study Procedures During Treatment

Patients must meet eligibility criteria on Day 1 to be treated as per this protocol.

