9.2 Bone Marrow Response Criteria

Complete Remission, MRD Negative (CR MRD)

- A bone marrow with < 5% blasts by morphology (hematologic complete remission);
AND
- MRD < 0.01% by flow;
AND
- No evidence of circulating blasts or extramedullary disease;
AND
- Recovery of peripheral counts (ANC > 500/ μ L and PLT count > 50,000 μ L).
- Qualifying marrow and peripheral counts should be performed within 1 week of each other

Complete Remission (CR)

- A bone marrow with < 5% blasts by morphology (hematologic complete remission);
AND
- No evidence of circulating blasts or extramedullary disease;
AND
- Recovery of peripheral counts (ANC > 500/ μ L and PLT count > 50,000 μ L).
- Qualifying marrow and peripheral counts should be performed within 1 week of each other.

Complete Response with Incomplete Count Recovery (CRi)

- A bone marrow with < 5% blasts by morphology (hematologic complete remission); **AND**
- No evidence of circulating blasts or extramedullary disease; **AND**
- Insufficient recovery of absolute neutrophil counts (ANC < 500/ μ L), and or insufficient recovery of platelets (PLT counts < 50,000/ μ l),

Partial Remission (PR)

- Complete disappearance of circulating blasts and one of the following:
- A decrease of at least 50% of blasts in the bone marrow with > 5% and \leq 20% blasts by morphology with recovery of peripheral counts (ANC > 500/ μ L and PLT count > 50,000 μ L)

Note: only patients who entered the study with \geq 20% blasts in the marrow may be assessed as PR

Stable Disease (SD)

Patient does not satisfy the criterion for either CR, CRi, PR or disease progression.

Progressive Disease (PD)

An increase of at least 25% in the absolute number of bone marrow or circulating leukemic cells, development of new sites of extramedullary disease, or other laboratory or clinical evidence of progression of disease.

Not Evaluable (NE)

Aplastic or severely hypoplastic marrow without any blast percentage. Bone marrow aplasia/hypoplasia is defined as overall marrow cellularity less than 10-20%. In this instance, marrow evaluation should be repeated every 1-2 weeks until response determination can be made.

Relapse

After documentation of remission, one bone marrow aspirate and/or biopsy showing \geq 5% leukemic blasts or pathological evidence of extramedullary disease.

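### Two of the five mandatory pre-infusion criteria in 6.1 are wrong as printed: the disease item has lost its negative, and the hemoglobin limit is in mg/dL and screens out no one

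*Combined protocol and SAP*

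**What the plan says.** Section 6.1 of the combined protocol and SAP sets minimal organ functions to be met before the infusion starts. It introduces them as criteria that patients must meet, so the list is mandatory. The five items cover oxygen, liver tests, hemoglobin, renal function and disease status.

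- The hemoglobin item reads "Hemoglobin > 8 mg/dL prior to infusion" and adds that patients may be transfusion dependent.
- The disease item, taken with the lead-in, requires patients to "Exhibit overt hematologic manifestations of relapse or persistent disease". Its second sentence says that evidence based primarily on flow cytometry, cytogenetics, chimerism or other molecular studies "does not by itself represent grounds for exclusion".

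Four other places bear on disease status.

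- 4.2.1 requires "Diagnosis of B-ALL in hematologic complete remission (defined as an M1 marrow, < 5% blasts", together with MRD of at least 0.01%.
- 5.2 states: "Patients must meet eligibility criteria on Day 1 to be treated as per this protocol".
- 6.1 itself states: "Cycle 2 of blinatumomab can be given to subjects who have achieved remission (< 5% marrow blasts) after Cycle 1", if MRD persists by flow. It also allows Cycle 2 for MRD-negative patients waiting on donor collection.
- 9.2 defines relapse as "After documentation of remission, one bone marrow aspirate and/or biopsy showing" at least 5% leukemic blasts, or pathological evidence of extramedullary disease.

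For hemoglobin there is nothing to compare: the organ-function limits in 4.2.5 are renal, hepatic and cardiac only.

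**The concern.** The trial treats patients in remission who have residual disease detectable only by sensitive assays. A criterion that they must show overt hematologic disease states the opposite of the population. A hemoglobin limit that no patient can fail is not a limit.

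Both intended checks have a purpose. The marrow that documents remission predates the infusion, so the disease item is where overt relapse since that marrow would be caught. Section 1.2 says cytokine release syndrome has been more prevalent with a higher leukemia burden, which is a reason not to start an infusion in a patient who has relapsed overtly in the interval. On hemoglobin, 1.2 reports anemia as the most frequent Grade 3 or higher event (36%) in the cited pediatric Phase 1/2 study.

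There is also a compliance cost. Eligibility data are among the items reviewed under 11.1.2. If the 6.1 list is copied verbatim into a treatment checklist, every correctly treated patient fails one item, and another item tells the auditor nothing.

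**Working it through.** No design figure is involved. The check is a comparison of texts, a unit conversion and a count of days.

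**Disease item**

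| Source | Status required at infusion |
|---|---|
| 4.2.1, applied on Day 1 by 5.2 | hematologic remission, < 5% blasts, MRD ≥ 0.01% |
| 6.1, Cycle 2 rule | < 5% blasts with MRD, or MRD negative and awaiting a donor |
| 9.2, marrow relapse | ≥ 5% leukemic blasts |
| 6.1, disease item as printed | overt hematologic relapse or persistent disease present |

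1. The ranges < 5% and ≥ 5% do not overlap, so a patient cannot meet 4.2.1 and be in marrow relapse as 9.2 defines it.
2. A patient in remission with MRD only meets 4.2.1 and fails the printed disease item. A patient in overt hematologic relapse meets the printed item and fails 4.2.1. Read literally, nobody passes both on Day 1.
3. The item's second sentence exempts flow, cytogenetic, chimerism and molecular evidence from being grounds for exclusion. An exemption from exclusion makes sense only if the first sentence excludes overt disease. The missing word is a negative.

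**Hemoglobin item**

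1. Printed limit: 8 mg/dL ÷ 1000 mg/g = 0.008 g/dL.
2. Against the evident intention: 8 g/dL ÷ 0.008 g/dL = 1000-fold too low.
3. The documents give no patient values, so assume extreme anemia of 2 to 5 g/dL, which is 2000 to 5000 mg/dL. Then 2000 ÷ 8 = 250 and 5000 ÷ 8 = 625. Even those patients would be 250 to 625 times above the printed limit.

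**Age of the marrow at the start of infusion**

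1. Cycle 1: 5.1.3 says "The screening procedures and assessments must be completed within 14-days of the Day 1 visit", so the marrow can be up to 14 days old on Day 1.
2. Cycle 2: 5.3.1 puts the end-of-cycle marrow on Day 28 ± 2, that is Days 26 to 30. The dosing table in 6.1 makes Days 29 to 42 treatment-free, so the earliest Cycle 2 Day 1 is Day 43 of Cycle 1.
3. Marrow age is then 43 − 30 = 13 days at least, 43 − 28 = 15 days on schedule, and 43 − 26 = 17 days at most for that earliest start.

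**Count:** two of the five items are defective.

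**The case against.** The strongest reply is that these are clerical slips with no shown route to different treatment. The second sentence of the disease item reveals the intent. Sections 4.2.1 and 5.2 and the Cycle 2 rule independently require remission or MRD negativity. A blood count with differential and a physical examination are required at screening, weekly during treatment and weekly in follow-up, so overt disease or severe anemia would probably be noticed. Section 7.0 directs transfusion by institutional standards. All of this stands, and it is why the practical effect is rated small.

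A second reply is that *overt hematologic* might qualify only *relapse*, leaving *persistent disease* to mean MRD. The Cycle 2 rule does use that phrase for flow-detected disease. Every Cycle 1 patient would then satisfy the item. This reading is strained, because the second sentence sets MRD-type evidence against the overt disease of the first. It also fails for Cycle 2: MRD-negative patients awaiting a donor, whom the same section allows to be treated, would not pass. No reading found makes the item correct for all permitted patients.

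Third, the 36% anemia figure is an on-treatment rate in relapsed or refractory patients. It says nothing about pre-infusion hemoglobin in patients in remission. That is fair: the figure is context for having a floor and does not measure harm from lacking one.

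Loss of a word or a wrong unit in reading the PDF cannot be fully excluded. Both lines are intact prose, however, with no redaction or broken table there.

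**Conclusion.** The concern holds. Two of the five mandatory pre-infusion criteria give the wrong instruction if followed as written. The disease item contradicts 4.2.1, 5.2, the Cycle 2 rule and its own second sentence; on the natural reading it leaves no eligible patient treatable. The hemoglobin limit is 0.008 g/dL, 1000-fold below 8 g/dL, and no other limit in 4.2 backs it up.

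The statement that nobody could be treated rests on reading *overt hematologic* as qualifying both relapse and persistent disease. The statement that every patient passes on hemoglobin rests on an assumed range of 2 to 5 g/dL for extreme anemia, with a margin so wide that the exact range does not matter. That 8 g/dL was intended is an inference for the sponsor to confirm.

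The practical effect is probably small, and the statistical design is untouched. The correction should still be made, because these are decision thresholds for starting treatment.

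**What to change.** Amend two items in 6.1, with the sponsor confirming both:

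1. Disease item: begin it with *Does not exhibit*, so that it requires the absence of overt hematologic relapse or persistent disease. Keep the second sentence, which then reads correctly.
2. Hemoglobin item: change the unit so that the limit is *> 8 g/dL*. Keep the note on transfusion dependence.

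Correct any treatment checklist or case report form that copies the list. The cost is two wording changes in an amendment, with no effect on design, sample size or analysis.

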6.2 Sample Collection and Processing for Minimal Residual Disease

Type of Sample	Instructions and Timing of Sample Collection
Bone Marrow Samples for Flow Cytometry MRD	
 At the end of each blinatumomab cycle (Day 28 \pm 2 days).
Bone Marrow Samples for Flow Cytometry MRD Bone Marrow Collection and Shipping Procedure	
 Bone marrow required for Flow Cytometry clinical evaluation MRD testing should be collected and shipped according to the standard procedures for the local institution. These samples will be evaluated by an approved Flow Cytometry Laboratory. Results of the clinical evaluation Flow Cytometry MRD testing at each timepoint will be communicated to each local institution by the approved Flow Cytometry Laboratory, and results should be entered into the EDC system by local Clinical Research Coordinators.
Bone Marrow Samples for High Throughput Sequencing MRD Samples	
 At time of enrollment prior to start of blinatumomab At the end of each blinatumomab cycle (Day 28 \pm 2 days). Baseline blast samples will be sent for B-cell and T-cell clonality assessment. If T-cell clonal sequences are detected on the baseline sample, T-cell clonality will continue to be sent along with B-cell clonality on subsequent samples. If no trackable T-cell sequences are detected, only B-cell HTS will be followed.

Type of Sample	Instructions and Timing of Sample Collection
Bone Marrow Sample for High Throughput Sequencing MRD Collection Procedure	
 Collect minimum of 2 mL of marrow into a syringe and place marrow into a large purple EDTA tube that are commonly used in all hospitals. Mix well Reposition marrow aspirates needle at least once during procedure to ensure the maximum quality of marrow
Specimen Labeling for High Throughput Sequencing MRD Sample	Each tube must be labeled with the study ID number, along with the date the sample was obtained. No personal identifying patient information should be included in the specimen or transmittal form.
Specimen Packaging and Shipping for High Throughput Sequencing MRD Sample	
Adaptive has fresh collection kits with EDTA tubes, ambient packs and pre-paid FedEx labels for domestic sites to use in this trial. Domestic samples should be shipped same day as collection at ambient temperature for overnight delivery to Adaptive. Adaptive is open to accept ambient samples Monday-Saturday. Include the completed and signed Test Requisition Form (obtained from Adaptive's diagnostic Portal) with shipment and send a sample shipment notification email to [contact].
 
Ship specimens to: Adaptive Biotechnologies Attn: CLIA Clinical Laboratory [name] [name]

6.3 Drug Information (Blinatumomab)

(Blincyto®, AMG103, MT103, recombinant bispecific antibody derivative)

6.3.1 Source and Pharmacology

Blinatumomab is a fusion protein composed of two single-chain antibodies (scFv), murine anti-CD19 scFv and murine anti-CD3 scFv. Through CD3 binding, blinatumomab recruits and engages T cells for redirected lysis of CD19-positive B cells, including those expressed with B-cell malignancies. T cells are bound by its anti-CD3 moiety, whereas B cells are bound by the anti-CD19 moiety. The subsequent serial lysis of multiple malignant cells by a single blinatumomab-activated T cell closely resembles a natural cytotoxic T cell reaction. Treatment with blinatumomab is associated with a rapid depletion of peripheral B cells, accompanied by T cell activation and a transient increase in cytokines.

Blinatumomab consists of a single chain of 504 amino acids with a molecular weight of approximately 54 kDa. The pharmacokinetics of Blinatumomab was assessed over a dose range from 5 to 90 mcg/m²/day (approximately equivalent to 9-162 mcg/day). Following continuous intravenous infusion, the steady state serum concentration (Css) was achieved within a day and remained stable over time. The estimated mean (SD) volume of distribution based on terminal phase (V_z) was 4.52 (2.89) L. The estimated mean (SD) systemic clearance was 2.92 (2.83) L/hour and the estimated mean (SD) half-life was 2.11(1.42) hours. Negligible amounts of blinatumomab were excreted in the urine at the tested clinical doses. Like other protein therapeutics, blinatumomab is expected to be degraded into small peptides and amino acids via catabolic

pathways. At the clinical doses of 9 mcg/day and 28 mcg/day for the treatment of adult relapsed/refractory ALL, the mean (SD) Css was 211 (258) pg/mL and 621 (502) pg/mL, respectively.

Currently there are no known drug incompatibilities or interactions with blinatumomab.

6.3.2 Pregnancy and Lactation

Pregnancy Category Unknown: The effect of blinatumomab on fertility has not been evaluated. Blinatumomab is not recommended in pregnant women and in women of childbearing potential not using contraception. It is not known whether blinatumomab or its metabolites are excreted in human milk. Women are not allowed to breastfeed while receiving blinatumomab.

6.3.3 Formulation and Stability

Blinatumomab is available as a 38.5 mcg preservative-free, white to off-white lyophilized powder for injection in 4 mL single-use vial. The agent is formulated with 3.68 mg citric acid monohydrate, 105 mg trehalose dihydrate, and 25.55 mg lysine hydrochloride, and 0.7 mg polysorbate 80, pH 7. The stopper of the vial is latex free.

6.3.4 IV Solution Stabilizer for Blinatumomab is not for reconstitution of blinatumomab; it is a component of the final intravenous product. The stabilizer is available as a 10 mL single-use vial of a preservative-free, clear, colorless-to-slightly yellow liquid solution. Each solution consists of 25 mM citric acid monohydrate, 1.25 M L-lysine hydrochloride, and 0.1% (w/v) polysorbate 80, pH 7. The stopper of the vial is latex free.

Store intact vials of blinatumomab and the IV solution stabilizer of blinatumomab refrigerated at 2° to 8°C (36° to 46°F). Protect from light. Shelf life stability studies of the intact vials of blinatumomab and stabilizer solution are on-going. The stability of the final prepared IV solution is 8 days when stored refrigerated at 2° to 8°C. For storage prior to administration, the prepared infusion solution must be kept at 2° C to 8° C (36°F to 46°F). The total storage and administration time must not exceed 8 days. Once at room temperature, discard the IV bag after 96 hours.

6.3.5 Guidelines for Administration

See Treatment and Dose Modifications sections of the protocol. Premedication with dexamethasone is required prior to the first dose of blinatumomab in the first cycle, prior to a step dose and when restarting an infusion after an interruption of 4 or more hours in the first cycle. Refer to the current USPI for volume calculations.

